Quantitative variables (gestational age, birth weight, age at frenotomy, heart rate pre and post-procedure, increase in heart rate post-procedure, oxygen saturation pre and post-procedure, decrease in oxygen saturation post-procedure, and duration of crying) are described using the mean, standard deviation and range; experimental vs control groups were compared with a Student's t-test. We assessed the equality of variances by using Levene's test and applied the result of the Student's t-test accordingly. Sex, the presence of crying, and adverse effects between the two groups are presented in percentages and compared using Fisher's exact test. Statistical significance was set for a p <0.05. To perform statistical analyses we used STATA version 16.1 (StataCorp, College Station, TX, USA).

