We conducted a prospective, randomized clinical trial. Our hospital Ethics Committee (CEIm-PSMAR) approved this study (reference code: 2023/10996). Prior to patient enrollment we obtained a signed informed consent from the neonate's parents. This study was conducted according to the ethics code of the Barcelona Medical Association and the principles of the Helsinki-Fortaleza Declaration 2013, at the neonatal unit of a tertiary care hospital in Barcelona (Spain) within an area of influence of approximately 400,000 people, which experiences approximately 1,400 births per year. The target population for this study, and thus, inclusion criteria were healthy full-term neonates born at our center or less than 15 days old referred for a frenotomy, who had ankyloglossia according to the Hazelbaker tool [39] (Figure 1) between September 2023 and June 2024. We assess for the presence of ankyloglossia as part of the routine neonatal evaluation using the Hazelbaker tool to evaluate its impact on tongue movement and on breastfeeding [39]. According to the Hazelbaker tool (see Figure 1), ankyloglossia exists if appearance scores 8 points or less and/or function scores 11 points or less. We offer a frenotomy to all patients with ankyloglossia. During the study period, if we identified a patient with ankyloglossia, we offered the patient's parents the opportunity to participate in this study.

Patients were enrolled if their parents agreed to and signed a written informed consent. We only included patients who were breastfed, as after randomization we may need to get colostrum. Enrolled patients were randomized into case or control group by simple random sampling using sequentially numbered containers. During the frenotomy the neonate was taken to the neonatal unit and monitored with a pulse-oximeter (COVIDIEN Nellcor Portable SpO₂ Patient Monitoring System PM10N, Covidien Ireland Limited, [name]) before, during and after the procedure. For both groups we swaddled, administered 1 mL of oral sucrose,

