and let the newborn suck for 2 minutes prior to the procedure. The control group had a 7 x 7 cm gauze pad with 1 drop (43.75 mg) of 100% pure LEO (Pranarôm España S.L.) placed 2 cm under their nose for 2 minutes prior to starting the frenotomy and for the duration of the procedure, whereas the experimental group had a gauze with 2 drops of colostrum of the patient's mother placed in the same way. We used two drops of colostrum but only one of LEO because the odor of colostrum is more subtle than that of LEO, and in our previous studies [32-33] we had used one drop of LEO, and that is how we routinely perform frenotomies. Once the procedure was completed, we removed the gauze pad and recorded vital signs, whether the baby cried or not, the seconds crying lasted, and the NIPS score on a data collection sheet. If a neonate cried, calming techniques such as holding, swaddling, and sucking were employed. A blinded observer assessed pain by means of the Neonatal Infant Pain Scale (NIPS) score (Figure 2) [40], crying duration, and whether there was a change in heart rate (HR) and/or in oxygen saturation (satO2) before and after the procedure.

In a previously published study where we compared performing frenotomies using complementary analgesia or not with inhaled LEO, we observed a mean (SD) crying time of 14.8 vs 24.6 (10.8 vs 27.6) seconds in favor of LEO [32]. In order to detect a difference of 10 seconds in crying time, we calculated that we needed a sample size of 71 patients per group in order to draw conclusions with a CI 95% and a power of 80%. We chose to evaluate pain by means of the increase of HR rather than via the NIPS score because in previous research, we obtained NIPS scores of 1.88-2.92 and 2.02-2.38, and a NIPS score less than 3 indicates no pain. We used the NIPS score to assess whether neonates exhibited pain when using inhaled colostrum instead of LEO.

We recorded demographic (sex, gestational age, birth weight, age in hours at the time of frenotomy) and clinical variables (HR and satO2 before, during, and after the

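### Heart rate and oxygen saturation are compared only by unadjusted t-tests, although a pre-procedure value that could sharpen both comparisons is already collected

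*SAP*

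**What the plan says.** The sample size paragraph of the protocol ranks the pain measures: "We chose to evaluate pain by means of the increase of HR rather than via the NIPS score". NIPS keeps a separate role: "We used the NIPS score to assess whether neonates exhibited pain when using inhaled colostrum instead of LEO". The intervention paragraph has a blinded observer assess, among other things, "whether there was a change in heart rate (HR) and/or in oxygen saturation (satO2) before and after the procedure", so pre and post values exist for every infant.

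The protocol's statistical analysis paragraph and the SAP, which have the same text, treat "heart rate pre and post-procedure, increase in heart rate post-procedure, oxygen saturation pre and post-procedure, decrease in oxygen saturation post-procedure" as separate quantitative variables. Each is compared between arms by a Student's t-test after Levene's test. No regression or other adjusted model appears. The protocol calls sex, birth weight and gestational age controlled variables, but no stated analysis uses them, and the pre-procedure HR and oxygen saturation (satO2) are not among them.

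The sample size was set on another outcome: "In order to detect a difference of 10 seconds in crying time".

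On timing, the gauze is "placed 2 cm under their nose for 2 minutes prior to starting the frenotomy". Post values come at the end: "Once the procedure was completed, we removed the gauze pad and recorded vital signs". The enrolment paragraph adds "During the frenotomy the neonate was taken to the neonatal unit and monitored with a pulse-oximeter", before, during and after the procedure. Nothing says whether the pre value is read before or after the gauze goes on.

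**The concern.** A t-test on the post value ignores the pre value. A t-test on the change subtracts it in full. Neither uses it in the proportion that the data support, which a model with the pre value as covariate does. What is lost is precision, not validity.

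This matters here for two reasons. The 71 per group was set on crying time, so nothing in the plan fixes the precision of the HR comparison, although HR is the measure preferred to NIPS. Both arms also receive an odour, so the width of the interval for the HR difference limits what can be said about colostrum against lavender oil (LEO).

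The timing gap bears on any analysis that uses the pre value. A reading taken after the gauze is in place is already exposed to the odour and is not a true baseline.

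**Working it through.** **The plan's own figure.** The protocol gives crying-time SDs of 10.8 and 27.6 seconds, so the common SD is √((10.8² + 27.6²)/2) = 20.96. For a 10-second difference, two-sided 5% and 80% power, the normal approximation gives 69 per group. The noncentral t gives 70 with pooled degrees of freedom and 71 with Welch degrees of freedom. The stated 71 is reproduced. It does not involve HR.

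**Inputs for HR.** From the documents: 71 per arm, 5% level (taken as two-sided), 80% power. Assumed, because the documents do not give them: pre/post correlation ρ of 0.3 to 0.9, and k = SD_post/SD_pre of 1, 1.25 or 1.5.

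**Formula.** Per infant, in units of SD_pre²:
- variance of the change: 1 + k² − 2ρk
- residual variance after adjustment: k²(1 − ρ²)

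The first minus the second is (1 − ρk)², which is never negative and is zero only when ρ = 1/k. That is the large-sample result for equal arms. Estimating the slope costs a factor of 1 + 1/138 = 1.007 at N = 142. So the net ratio, adjusted to change score, is 1.007 × k²(1 − ρ²)/(1 + k² − 2ρk).

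| Net variance ratio | ρ = 0.3 | ρ = 0.5 | ρ = 0.7 | ρ = 0.9 |
|---|---|---|---|---|
| k = 1 | 0.655 | 0.755 | 0.856 | 0.957 |
| k = 1.25 | 0.790 | 0.899 | 0.988 | 0.957 |
| k = 1.5 | 0.878 | 0.971 | 1.005 | 0.783 |

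**Interval width** is the square root of the ratio. At k = 1 it changes by −19.1%, −13.1%, −7.5% and −2.2%; at k = 1.5 by −6.3%, −1.4%, +0.3% and −11.5%.

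**Equivalent sample size** at k = 1 is 71 divided by the ratio: the change-score test would need 108, 94, 83 or 74 per arm to match.

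**Difference detectable with 80% power** at k = 1, in units of SD_pre:
- change score, 2.80 × √(2(1 − ρ) × 2/71): 0.556, 0.470, 0.364, 0.210
- adjusted, 2.80 × √((1 − ρ²) × (2/71) × 1.007): 0.450, 0.409, 0.337, 0.206

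**Simulation check** (6000 trials of 71 + 71, HC3 standard errors). Variance ratios were 0.64, 0.76, 0.85 and 0.96 at k = 1, and 0.89, 0.96, 1.01 and 0.79 at k = 1.5. Type I error was 4.2% to 5.0% adjusted and 4.4% to 5.3% for the change score. At k = 1, where the change score has about 80% power, the adjusted test had 93%, 89%, 84% and 81%.

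**satO2**, with assumed latent means of 98 and 97, SD_pre of 2, and values rounded and capped at 100 (5000 trials). Ratios at latent ρ of 0.3, 0.5, 0.7 and 0.9 were 0.704, 0.793, 0.903 and 0.992 with SD_post 2, and 0.862, 0.951, 1.006 and 0.857 with SD_post 3.

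**Against the post-value t-test**, the net ratio is 1.007 × (1 − ρ²) = 0.92, 0.76, 0.51 and 0.19.

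**Late pre reading.** If the two odours shift the pre value by s between arms, the change-score estimate moves by s and the adjusted estimate by ρks, which is 0.3s to 0.9s at k = 1. Neither is then clean.

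**The case against.** The strongest reply is that nothing here is an error. Both planned tests are valid, and the change score already uses the pre value. The benefit rests on a correlation and SDs that the documents do not give. At ρ = 0.9 with equal SDs, or at k = 1.5 with ρ between 0.5 and 0.7, it is negligible. HR is preferred only to NIPS and is nowhere named the primary outcome. The sized outcome, crying time, has no baseline. Enrolment is dated September 2023 to June 2024 and the text is in the past tense, so the analysis may be finished. Finally, the guarantee for a main-effects model needs equal arms or equal slopes, and simple randomisation does not force equal arms.

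Most of this stands as a limit on size: the gain is a range, it may be small, and it may have to be reported as post hoc. It does not remove the point, because the possible loss is about 0.7% of variance and the data are already in hand. On allocation, the target is 1:1 and simple randomisation tends to it. In simulated splits of 60/82 and 55/87, with slopes of 0.5 in both arms or 0.3 and 0.7, the ratio to the change score stayed at roughly 0.76 to 0.79. The timing objection also stands, and it weighs on the planned change score at least as much as on the adjusted model.

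**Conclusion.** The point holds, as a loss of precision and not of validity. Over the assumed range for HR, adjustment cuts the variance relative to the change score by up to about 35% (1 − 0.655). It costs at most about 0.7%, when ρ equals SD_pre/SD_post (0.80 at k = 1.25, 0.67 at k = 1.5). For satO2 the simulated range runs from a 30% fall to a 0.6% rise.

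These figures rest on 71 per arm in near-equal allocation, on assumed correlations and SD ratios, and on a pre value read before the gauze is placed. Where this trial lies within the range cannot be told from the documents, so confidence in the size of the gain is moderate. The change is worth making but is not essential to the trial's validity.

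**What to change.** 1. State when the pre value is read, and use a reading taken before the gauze is placed.
2. Estimate the arm difference in HR from a linear model of the post-procedure value on arm and pre-procedure value, with a robust standard error and a 95% confidence interval. Do the same for satO2.
3. Keep the change-score t-test as a sensitivity analysis.
4. If only a reading taken after gauze placement exists, do not adopt the adjusted model. The planned post-value t-test is then the comparison that does not depend on that reading.
5. If the data have already been analysed, keep the planned t-test as the planned result and report the adjusted estimate beside it, labelled post hoc.

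The cost is one Stata model and one degree of freedom per outcome, plus one sentence on timing. No new data are needed if a pre-gauze reading exists, and the 71 per group is unaffected.
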